Protocol

The prediction of failure rate of dental implants

NCT number: Unknown yet

Document date: 21-9-2018

During the past decades, dental implant therapy has developed into a successful treatment option for patients confronted with both partial and complete edentulism. Based on the literature, the survival rate of dental implants, which is defined that the dental implants are still in the mouth after insertion, is around 95% in the 5-year follow-up and around 90% in the 10-year follow-up [1-3]. The success rate of dental implants, which is defined as dental implants in function, with good hard and soft tissue physiology and user satisfaction ranges from 85.2% to 88.7% in the follow-up of up to 20 years [4-6]. This indicates that both the success rate and survival rate of dental implants is high. However, both survival rates and success rates vary across patients with different profiles. The expense of dental implant treatment is high and implant placement is a surgical procedure which is invasive and thus risky for the patients' health. Once the failure of dental implants occurs, it may cause some severe negative consequences for patients. For example, the failure will cause a financial loss for patients and a possible shock concerning both mental and physical aspects. To reduce these risks it is important and necessary for clinicians to be able to predict the risk of the failure of dental implants of individual patients before they undergo dental implant treatment.

Aim:

The aim of the project is to identify important risk factors for failure of dental implants and to develop a prediction model for the failure rate of dental implants at follow-up as a tool for clinicians to establish patients individual risk profile.

Methods:

Study design

The study is a retrospective design. The clinical data of all the adult patients who were referred to the Department of Oral Implantology and Prosthetic Dentistry, Academic Centre for Dentistry Amsterdam (ACTA) at their first intake for placement of dental implant(s) from September 2009 to September 2013 are collected retrospectively from the clinical data management system of ACTA in the study.

Predictors

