The univariate and multivariate Cox regression analysis is used to identify important risk factors for the failure of dental implants and to develop the model. Then, the performance of the models, in aspects of calibration and discrimination, is assessed. Calibration is defined as the agreement between predicted outcomes and observed outcomes. For assessment of calibration, the included implants are separately grouped into deciles based on their predicted risk of failure. The calibration of the model is assessed by plotting the predicted risk of failure against 1 minus the individual Kaplan-Meier estimate for each decile in the follow-up. Discrimination is defined as the ability of the model to differentiate between those with and without outcome events. The discrimination of the model in the follow-up is assessed with the concordance index (C-index). Then, the model is converted to a score chart and line chart in order to facilitate the calculation of the failure rate of implants. The score of each included predictor is produced by the regression coefficients being divided by the smallest regression coefficient among the predictors and subsequently rounded. Finally, the clinical values of the model are assessed, using prevalence, sensitivity, specificity, positive predictive value (PPV), and negative predictive value (NPV) of the model at the optimal cutoff score.

All the statistical procedures are performed with SPSS software 25.0 (IBM, New York, the USA) and R software 3.2.3 (R Development Core Team, Vienna, Austria).

What is already known:

Recently, there are many studies focusing on the evaluation of survival rate of implants based on longitudinal cohorts. However, they mainly reported the values of the failure rate of implants in the follow-up (like 5-year survival rate) or compared the failure rate of different types of implants. These types of studies are beneficial for the groups of patients but not for the individual patients. Also, there are several studies focusing on the prognostic factors that may be associated with the survival rate of dental implants. But these studies belonged to prediction factor studies instead of prediction modeling studies. The findings in these studies are difficult to directly apply to clinical practice.

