However, there is a very limited number of studies focusing on the prediction of survival rate (or failure rate) of implants in the follow-ups. For example, Chuang et al. (1) used a clustered marginal approach to predict the survival rate in 2002 and found that among those who had a delayed procedure, did not smoke, and underwent a two-stage implant procedure, the predicted 1- and 5-year survival rates were 97.2% and 93.4%, respectively. For those who had an immediate implant placed, smoked, and underwent a one-stage procedure, the predicted survival rates were 58.5% and 27.6%, respectively. In 2006, Chuang and Cai (2) used Cox proportional hazards frailty model to predict the future implant survival based on some predictors including smoking status, the timing of placement of the implant and implant staging.

In this study, they predicted that for a non-smoking individual with 2 implants placed, an immediate implant and in one stage, the probability that 1 implant would survival 12 months was 85.8% and the joint probability of surviving for 12 months was 75.1%. If 1 implant was placed earlier and had survived for 12 months, then the second implant had an 87.5% chance of surviving 12 months. However, in these two studies, the authors only included a small number of predictors and did not develop a score chart for the individual patients. Also, the performance of the models was not assessed.

What is the project will add:

The project can provide clinicians with the predicted probability of the failure rate of dental implants of each individual patient preoperatively. The model may be helpful for clinicians to make decisions about the postoperative care for the patients. Also, the model can help shape the patients' expectations about the survival of dental implants.

What is new:

In the project, we will use some more predictors to predict the survival rate of dental implants to make the prediction model more accurate. Also, we will develop a score chart for clinicians. In this score chart, clinicians can easily calculate the sum score of each patient and find out the corresponding predicted probability of the failure rate of dental implants of each individual patient. The score chart is very easy-to-use in the clinical practice. Besides, in this project, the methodology (the prediction model developed with Cox regression analysis) is novel in dentistry.

References:

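### Model performance is to be measured only in the cohort that fits the model, with no internal validation, optimism correction or shrinkage

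*Combined protocol and SAP*

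**What the plan says.** Under Study design there is one data source, a single centre's records: "from September 2009 to September 2013 are collected retrospectively from the clinical data management system of ACTA in the study". No second cohort and no split of this one is mentioned.

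Under Statistical analysis the plan runs in this order:

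- Univariate and multivariate Cox regression identifies risk factors and builds the model. No selection threshold is given.
- "Then, the performance of the models, in aspects of calibration and discrimination, is assessed".
- Calibration: "For assessment of calibration, the included implants are separately grouped into deciles based on their predicted risk of failure". Predicted risk in each decile is plotted against one minus the Kaplan-Meier estimate.
- Discrimination is measured by the C-index.
- The model becomes a score chart: "The score of each included predictor is produced by the regression coefficients being divided by the smallest regression coefficient among the predictors and subsequently rounded".
- Prevalence, sensitivity, specificity and the predictive values are given, ending with "negative predictive value (NPV) of the model at the optimal cutoff score". The criterion that makes a cutoff optimal is not stated.

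The section on what is already known faults earlier prediction models: "Also, the performance of the models was not assessed". Under What is new, clinicians are to use the chart to "find out the corresponding predicted probability of the failure rate of dental implants of each individual patient".

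**The concern.** A model looks better in the data that produced it than in new patients, because its coefficients, any selected predictors and any cutoff chosen on those data have been tuned to that sample's noise. Following the plan as written gives only this apparent performance.

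What is at stake is the project's main product. The chart is to supply individual probabilities before surgery, inform postoperative care and shape patients' expectations. If the model is overfitted, high predicted risks will be too high and low ones too low, and nothing in the plan would show it. The protocol also expects that using more predictors will make the model more accurate. With a fixed number of events, more candidates increase optimism, so apparent figures cannot support that expectation.

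**Working it through.** **1. Data behind each measure.** For calibration, use of the development data is explicit, since the deciles are formed from the included implants. For the C-index and the cutoff accuracy it is an inference, but the plan offers no other data.

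**2. Why the calibration plot cannot show overfitting.** Let b be the unpenalised Cox estimate, so the partial-likelihood score satisfies U(b) = 0. The calibration slope g is found by refitting with the single covariate b'x. Its score at g = 1 is b'U(b) = 0, so g = 1 in the development data whatever the degree of overfitting. The plot can still show wrong functional form or non-proportional hazards.

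**3. Size.** The plan states no sample size, event count, number of candidates or target C-index, so there is no figure to reproduce. The size was explored by simulation under these assumptions:

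- 25, 50, 100, 200 or 300 events; 12% failing by 5 years (the literature success rates in the introduction, 85.2% to 88.7%, imply 11.3% to 14.8% non-success).
- 10 or 20 independent binary candidates, each with 30% prevalence.
- Weaker predictors: six true hazard ratios of 1.5. Stronger predictors: three of 2.66 plus three of 1.5. The 2.66 comes from the 5-year survival figures quoted from the 2002 study: ln 0.276 / ln 0.934 = −1.2874 / −0.06828 = 18.9, spread over three factors, 18.9^(1/3) = 2.66.
- All candidates entered, or univariate p < 0.10 followed by backward p < 0.05.
- Complete 5-year follow-up, independent implants, and a cutoff maximising Youden's index on the rounded score.

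This gives 5 × 2 × 2 × 2 = 40 settings, with 400 development sets each, every model being tested on 3,000 new implants. Sets in which nothing was selected were excluded (up to 119 of 400 at 25 events). Ranges across settings:

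| Events | C-index, apparent minus new | Calibration slope in new data | Sensitivity lost at cutoff |
|---|---|---|---|
| 25 | 0.07–0.22 | 0.17–0.69 | 0.13–0.37 |
| 50 | 0.03–0.14 | 0.32–0.85 | 0.07–0.24 |
| 100 | 0.02–0.08 | 0.51–0.91 | 0.04–0.15 |
| 200 | 0.01–0.05 | 0.70–0.95 | 0.03–0.09 |
| 300 | 0.01–0.03 | 0.77–0.97 | 0.01–0.06 |

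The development-data slope was 1.00 throughout. Specificity fell by at most 0.05. Rounding the coefficients cost at most 0.005 of C-index, so rounding is not a shown source of optimism.

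**4. What a clinician would see.** Top risk decile, 50 events, 20 candidates with selection, predicted versus observed 5-year failure:

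| Predictors | Development data | New data |
|---|---|---|
| Weaker | 26.1% vs 26.2% | 26.3% vs 17.0% |
| Stronger | 39.2% vs 39.4% | 39.0% vs 31.7% |

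The development plot looks almost perfect in both cases.

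**5. A different set of assumptions.** A separate simulation used standard normal candidates, four of them true with log hazard ratio 0.3, univariate screening at p < 0.10, and 10 to 30 candidates. Apparent performance exceeded new-data performance in all 12 settings. At 80 events and 20 candidates the C-index was 0.685 apparent and 0.632 in new data, the slope 0.72, and Youden's index 0.322 against 0.192. At 300 events and 10 candidates the gap was small: 0.667 against 0.658, slope 0.95.

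**6. Implants needed for 200 events.** At 14.8% non-success, 200 / 0.148 = 1,351. At 5% lost by 5 years, 200 / 0.05 = 4,000.

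**The case against.** The strongest reply accepts the omission and disputes its size.

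- **The upper ends come from entering every candidate.** A rerun with 20 candidates and weaker predictors gave C-index optimism of 0.215, 0.139, 0.045 and 0.031 at 25, 50, 200 and 300 events without selection, and 0.130, 0.092, 0.031 and 0.019 with it. The plan's wording suggests selection, and the candidate list is first screened through literature, guideline and experts; 14 null predictors out of 20 is an assumption. This stands as a caution against reading the maxima as likely. It does not remove the problem: optimism is present with and without selection.
- **The 25-event row is conditional on a model being produced.** Counting empty models as zero optimism lowers the figures with selection (weaker predictors) from 0.104 to 0.077 (10 candidates) and from 0.130 to 0.107 (20 candidates). This stands.
- **With several hundred events and few candidates the optimism may be negligible.** True, but the plan gives no assurance of being in that range and no way to find out.
- **The implant counts are a rough guide.** Neither rate is the plan's own endpoint of peri-implantitis, mobility or removal, so they do not show that 200 events is out of reach. Complete 5-year follow-up is also idealised: intake ran to September 2013, baseline is the later suprastructure placement, and the document is dated 21 September 2018. Both points stand.
- **The stated aim is to develop a model, and the score is partly tested through its cutoff accuracy.** Correct, but those accuracy figures are apparent as well, and the chart is presented for use with individual patients.

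**Conclusion.** The concern holds and should be settled before the analysis is run. The omission is certain from the text, and so is the direction of the bias in expectation. Its size is undetermined. Under the simulation assumptions it ranges from minor (C-index optimism about 0.01, new-data slope 0.95 or above, in the most favourable settings at 200 to 300 events) to serious (optimism up to 0.14 and slope down to 0.32 at 50 events, worse at 25). The simulations treat implants as independent. Several implants from one patient carry less information, so the true optimism could be larger than shown.

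**What to change.** Add bootstrap internal validation to the Statistical analysis section:

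- Use at least 200 samples, resampling patients, not implants.
- In each sample, repeat every data-driven step: any predictor selection, fitting, score rounding and choice of cutoff. This requires the selection rule and the cutoff criterion to be written down first.
- Report the optimism-corrected C-index, calibration slope, and sensitivity, specificity, PPV and NPV at the cutoff, for both the regression equation and the rounded score chart.
- Multiply the coefficients by the bootstrap shrinkage factor s and re-estimate the baseline hazard before mapping scores to predicted risks. The points do not change, since (s·b_j)/(s·b_min) = b_j/b_min; only the risk attached to each score does.

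The remedy was checked with 200 resamples on up to 60 simulated sets per setting, using 20 candidates with selection. Corrected against new-data C-index was 0.567 vs 0.560 (weaker predictors) and 0.687 vs 0.690 (stronger) at 50 events, and 0.579 vs 0.581 and 0.707 vs 0.712 at 100 events. Corrected sensitivity was within 0.01. The corrected slope was within 0.06 except at 50 events with weaker predictors, where it was 0.61 against 0.43, so with few events shrinkage may still be too mild. The check used independent implants, so resampling by patient was not itself tested.

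The cost is analysis code in R, which the plan already names, and no new data. The reported performance will look somewhat less favourable. Internal validation does not replace external validation before clinical use.

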The initial list of potential predictors for the failure of implants is first determined based on previous literature and the Dutch Clinical Practice Guideline (KPR). Then, the list of the predictors is sent to the international experts from the International Team for Implantology (ITI) for further screening. Finally, the short list of the potential predictors is determined based on the experts' opinions and the availability of the predictors in the clinical data management system of ACTA. The potential predictors include five domains: patients' demographic characteristics, lifestyle habits, general health, dental health, and implant characteristics.

Outcomes

The outcomes include the follow-up time of implants and whether the failure of the implants is observed at the follow-up. The follow-up time is defined as a period in days starting from the date at the placement of suprastructure (baseline) to the date at the last follow up time or the

date when the failure is observed. The failure of implants is defined as the presence of peri-implantitis, presence of mobility of implants, or removal of the implants for any reasons, for instance, unacceptable performance in aspects of function, tissue physiology, esthetics, and patients' satisfaction after placement of suprastructure.

Statistical analysis

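### Calibration is judged only from a ten-point decile plot in the development data, with no interval, no numerical measure and no fixed time point

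*Combined protocol and SAP*

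**What the plan says.** The Statistical analysis section defines calibration as agreement between prediction and observation and then gives a single procedure. First, "the included implants are separately grouped into deciles based on their predicted risk of failure". Then: "The calibration of the model is assessed by plotting the predicted risk of failure against 1 minus the individual Kaplan-Meier estimate for each decile". The only reference to time is that the observed quantity is "1 minus the individual Kaplan-Meier estimate for each decile in the follow-up"; no year is named.

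The other performance measures are the C-index and, at a cutoff score, prevalence, sensitivity, specificity and predictive values. None of these measures calibration. No split sample, resampling or external data set is mentioned, so the plot is drawn in the implants used to fit the model.

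The sections on what the project will add and what is new say that clinicians will read an individual patient's failure probability from a score chart, before surgery. The section on earlier work faults two published models because their performance was not assessed.

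**The concern.** A tool that gives a patient a percentage depends on that percentage being right. Here, whether it is right would be decided by looking at ten points with no intervals. A reader could not tell a real departure from chance scatter, or real agreement from a plot too imprecise to show disagreement.

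Two further gaps add to this. A Cox model predicts a different risk at each time, so a plot without a stated horizon can be drawn at whichever time looks best. And because the plot is drawn in the development data, it shows apparent calibration, which is usually better than what new patients would experience.

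**Working it through.** **Inputs from the protocol**
- Ten groups, with the implant as the unit (Statistical analysis).
- Implant survival "is around 95% in the 5-year follow-up and around 90% in the 10-year follow-up" (opening paragraph): loss of about 5% and 10%.
- Success "ranges from 85.2% to 88.7% in the follow-up of up to 20 years" (same paragraph): non-success of 100 − 88.7 = 11.3% to 100 − 85.2 = 14.8%.
- Study outcome (Outcomes): "The failure of implants is defined as the presence of peri-implantitis, presence of mobility of implants, or removal of the implants for any reasons". This is wider than loss, so 5% may understate it. The success figures are conceptually closer but extend to 20 years.
- Cohort size and number of failures: not given. Study design states only that patients were referred "at their first intake for placement of dental implant(s) from September 2009 to September 2013".

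The plan states no calibration precision, so there is no figure to reproduce. The number of implants N is an assumption, shown as a range.

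**Step 1. Precision of an average decile.** With n = N/10, expected failures = n·p and the 95% half-width = 1.96·√(p(1−p)/n). For N = 1,000 and p = 11.3%: n = 100, 11.3 failures, and 1.96·√(0.113·0.887/100) = 6.2 points.

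Expected failures per decile; half-width in percentage points:

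| N (assumed) | p = 5% | p = 11.3% | p = 14.8% |
|---|---|---|---|
| 500 | 2.5; 6.0 | 5.7; 8.8 | 7.4; 9.8 |
| 1,000 | 5.0; 4.3 | 11.3; 6.2 | 14.8; 7.0 |
| 2,000 | 10; 3.0 | 22.6; 4.4 | 29.6; 4.9 |
| 5,000 | 25; 1.9 | 56.5; 2.8 | 74; 3.1 |

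At p = 10% the half-width is 10.7 points with 300 implants, 7.6 with 600 and 5.9 with 1,000. Censoring and several implants per patient are ignored, so these are best cases. An assumed design effect of 1.5 widens each interval by √1.5 − 1, about 22%.

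**Step 2. Low and high deciles.** Assume a normal Cox linear predictor with SD 0.8 and mean risk 11.3%. The lowest decile then has a true risk of 2.3% and the highest 31.9%.

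| N (assumed) | Lowest decile: failures; half-width as % of its risk | Highest decile: failures; half-width as % of its risk |
|---|---|---|
| 500 | 1.2; 179% | 16; 40% |
| 1,000 | 2.3; 127% | 32; 29% |
| 2,000 | 4.7; 90% | 64; 20% |
| 5,000 | 11.6; 57% | 160; 13% |

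**Step 3. Would numerical measures alone solve it?** Not in the development data. The Cox estimate β̂ solves U(β̂) = 0, where U is the partial-likelihood score. Refit with the linear predictor as the only covariate, with coefficient γ: the score at γ = 1 is β̂ᵀU(β̂) = 0, so the estimated slope is exactly 1 however overfitted the model is. A simulation agrees (300 data sets; assumed 600 implants, about 11% events, ten predictors of which eight are noise): the apparent slope was 1.000 every time, while the mean slope in new data was about 0.65. Calibration-in-the-large likewise sits near its ideal value.

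**Step 4. Does a smooth curve help?** In simulation it estimated risk with about 40% less error than decile points at every size tried. At 600 implants the error was 2.2 against 3.8 points, and 1 − 2.2/3.8 = 42%. The curve borrows strength between neighbouring risks, so the gain assumes that true calibration changes smoothly with predicted risk.

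**The case against.** Grouped plots of predicted risk against Kaplan-Meier are a recognised calibration display for survival models, and intervals can be added when the results are reported. The cohort covers all consenting adult referrals to a department over four years and may run to thousands of implants. The outcome includes peri-implantitis and may be well above 5%. On that view the plot could be adequate. A plot can also reveal curved miscalibration that a single slope would miss.

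Much of this stands. A reader might infer that the decile points are simply too noisy to show whether the predicted risks are right. The documents do not support that, because they give neither the number of implants nor the number of failures, and at 5,000 implants the average-decile half-width is only 1.9 to 3.1 points. Nor does grouping by predicted risk lose the order between deciles; only the order within a decile is lost. A reader might also suppose that tied predictions make the decile edges arbitrary, but the Predictors section lists five domains and no coding, so this cannot be judged.

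What the objection does not answer is independent of cohort size: the plan specifies no interval, no numerical measure, no horizon and no correction for assessing the model in its own data.

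**Conclusion.** The concern holds in a conditional form. As written, the calibration conclusion would rest on visual judgement of ten points without intervals, at an unstated time, in the development data.

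The imprecision depends on an assumed cohort size. With up to about 1,000 implants and risks of 5% to 15%, most decile points would be imprecise. Low-risk deciles would remain so at larger sizes, with a half-width still 57% of the lowest decile's own risk at 5,000 implants. Upper deciles at several thousand implants would be reasonably precise. The decile-specific figures also rest on the assumed spread of the linear predictor.

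The analysis can be run as planned, so this is a change that should be made rather than a fatal fault. Adding an uncorrected slope or calibration-in-the-large would not be an improvement, because both would look good by construction.

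**What to change.** In the Statistical analysis section:

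1. State the prediction horizon for calibration, and the number of implants, patients and failures available at it.
2. Make the primary assessment a smooth calibration curve at that horizon: a spline regression of the outcome on the log-log transformed predicted risk, allowing for censoring. Give it a confidence band from a bootstrap that resamples patients, since implants are clustered within patients.
3. Keep the grouped Kaplan-Meier points as an overlay, with confidence intervals, and use fewer groups where failures are sparse.
4. Report the calibration slope, calibration-in-the-large and integrated calibration index only after optimism correction. Repeat the whole model-building process, including predictor selection, in each patient-level bootstrap sample. The band in item 2 shows sampling variability and does not remove optimism, so the corrected measures should be read beside the curve.

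This needs no new data and can be done in R, which the plan already uses. The cost is a little more analysis and reporting, and calibration results that will probably look less favourable than the uncorrected plot.

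### The probabilities that clinicians will read from the rounded score chart and line chart have no planned calibration check, and the step from total points to probability is not described

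*Combined protocol and SAP*

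**What the plan says.** The Statistical analysis section of the combined protocol and SAP sets out four steps in order.

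1. Cox regression is used to select risk factors and build the model.
2. "Then, the performance of the models, in aspects of calibration and discrimination, is assessed". For calibration, implants are grouped into deciles of predicted risk: "The calibration of the model is assessed by plotting the predicted risk of failure against 1 minus the individual Kaplan-Meier estimate for each decile". Discrimination is measured by the C-index.
3. "Then, the model is converted to a score chart and line chart in order to facilitate the calculation of the failure rate of implants". Each predictor's points are its coefficient "divided by the smallest regression coefficient among the predictors and subsequently rounded".
4. Last come prevalence, sensitivity, specificity, PPV and "negative predictive value (NPV) of the model at the optimal cutoff score".

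Under What is new, the chart is the tool for practice: the user adds up the points to "find out the corresponding predicted probability of the failure rate of dental implants of each individual patient".

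**The concern.** Rounding coefficients to whole multiples of the smallest one produces a coarser model than the one fitted. The plan's two performance measures are placed before that step, and neither is repeated after it. The measures that follow describe classification at a single threshold. They do not test whether the probability printed against each score agrees with observed failure.

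The patient is given the chart's number. Without a check on the chart, readers would take the calibration plot and C-index of the fitted Cox model as evidence for it. The protocol itself, under What is already known, faults two earlier prediction studies because their models' performance was not assessed.

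A second gap adds to the first. The section does not say how the line chart turns total points into a probability. Two routes fit the text: multiply points back by the smallest coefficient and apply the model's baseline, or fit a new model on the total score. They can give different probabilities.

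**Working it through.** **Inputs.** The documents give no coefficients, number of predictors, event count or baseline risk, so there is no figure of the plan's to reproduce. The order of the steps comes from the text. Every number below is an assumption chosen to show the mechanism.

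**Check of the text.** The decile grouping uses predicted risk and is described before any score exists. The conversion is introduced as the next step, and the cutoff measures as the final one. No later sentence applies calibration or the C-index to the score. That these measures refer to unrounded coefficients is an inference from this order; nothing in the documents contradicts it.

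**Worked example.** Assume six yes/no predictors with log hazard ratios 0.35, 0.50, 0.52, 0.60, 0.85 and 0.90, and a 3% risk when none is present.

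- Points = round(b / 0.35). The ratios are 1.00, 1.43, 1.49, 1.71, 2.43 and 2.57, giving 1, 1, 1, 2, 2 and 3 points.
- Model risk = 1 − 0.97^exp(sum of b).
- Lowest risk at 5 points: 0.60 + 0.90 = 1.50, exp(1.50) = 4.48, risk 12.8%.
- Highest risk at 5 points: 0.35 + 0.50 + 0.52 + 0.85 = 2.22, exp(2.22) = 9.21, risk 24.5%.
- At 4 points the same calculation runs from 10.1% (0.35 + 0.90 = 1.25) to 17.9% (0.50 + 0.52 + 0.85 = 1.87).

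The two ranges overlap, so a 4-point profile can have a higher model risk than a 5-point one.

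Weight all 64 patterns by an assumed, independent 30% prevalence per predictor:

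| Quantity | Full model | Points × 0.35, no refit |
|---|---|---|
| Mean risk | 11.1% | 10.4% |
| Mean absolute difference from full model | – | 1.4 points |
| Risk with all six present (10 points) | 71.5% | 63.5% |

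With a refit on total points, the mean absolute difference is about 1.3 points. The C-index, approximated for a binary outcome, falls from 0.716 to 0.710.

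**Wider simulation.** Take 200 data sets, six binary predictors at 30% prevalence, coefficients drawn from 0.3 to 1.2, baseline cumulative hazard 0.05 and no refit. The median across data sets of the mean absolute risk difference was 2.0 points, of the 95th percentile 6.8 points, and of the maximum 11.8 points. The median C-index moved from 0.731 to 0.729.

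**Outer bound without a refit.** For k binary predictors the log-hazard error is at most 0.5 × (smallest coefficient) × (k − 1).

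- Smallest coefficient 0.2, k = 3: the bound is 0.2, a hazard factor of 1.22. A 10% model risk could read 8.3% to 12.1%.
- Smallest coefficient 0.4, k = 5: the bound is 0.8, a factor of 2.23. A 10% model risk could read 4.6% to 20.9%.

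The possible loss therefore grows with the smallest retained coefficient and the number of predictors, neither of which is known before the fit.

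**The case against.** The strongest reply is that the expected effect is modest. Discrimination hardly changes, and average risk errors are 1 to 2 points. The worked example also has three of its six ratios (1.43, 1.49, 2.43) just below a rounding boundary. The 24.5% profile has all three of those predictors plus the smallest one, and it makes up only 0.4% of implants at 30% prevalence. This stands, and it limits how serious the point is.

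The score is also not wholly unassessed. PPV and NPV compare observed failure on either side of a score threshold. That stands too, but they do so at one cutoff and do not test the printed probabilities.

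A reader might infer three stronger things that the documents do not support.

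- *That the reported performance would belong to a model nobody uses.* The points are a direct rounding of that model. Full-model performance is also a legitimate result in a study that aims to identify risk factors.
- *That the investigators intend not to refit on the total score.* The section is silent on how the line chart is built, and a refit is compatible with the text.
- *That the 12.8% to 24.5% spread shows miscalibration.* It shows lost resolution. The average model risk at 5 points is 16.8% under the same assumptions. A chart printing about that would look well calibrated, and a decile plot would not reveal the spread.

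**Conclusion.** The gap is real. If the plan is followed as written, the probabilities on the delivered chart are not checked for calibration, and their derivation from total points is unspecified. This rests on the order of steps in the Statistical analysis section and on the use of the chart described under What is new, not on the illustrations.

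The size in this study cannot be known from the documents. Under the assumed inputs, average errors are about 1 to 2 percentage points with larger errors for some profiles, and the change in C-index is negligible. With a small minimum coefficient and a refit, the loss could be trivial. The plan as it stands would not show which case applies.

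This is a should-fix point. It does not invalidate the model, and the same data still allow it to be closed.

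**What to change.** In the Statistical analysis section, after the conversion step, add text to this effect: *A Cox model with total points as the only covariate will be fitted, and the line chart will be drawn from that fit. The calibration plot and C-index specified for the full model will be repeated for the score chart at the same follow-up time and reported beside the full-model results. Chart and full-model predicted risks will be compared across implants, including the spread of full-model risk within each score.*

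The last sentence is needed because the calibration plot alone cannot show lost resolution. If there are too few distinct totals to form deciles, adjacent score values can be grouped instead.

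The cost is a wording change and a few lines of R, with no new data. The reported performance of the chart may be slightly less favourable than that of the full model.
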